#### **10.2.5. Treatment Week 12 (Visit T4; ± 3 days)**

If the patient is withdrawing early from the study at this visit, proceed to [Section 10.2.8](#) for the list of the required assessments.

If the patient is withdrawing from IMP treatment at this visit, proceed to Section 10.2.8 for the list of the required assessments. The patient will be asked to continue to be followed for safety using the protocol-specified visit schedule. If the patient consents for follow-up, schedule the next protocol-specified visit.

Patients who do not provide consent to continue to return to the clinic for safety assessments after withdrawing from IMP treatment will be asked to participate in phone calls from the site at

protocol-specified visits, or at a minimum at 52 weeks, to inquire about the patient's current health status and collect information on AEs (eg, recent procedures, hospitalizations, and if the patient has died, the cause of death). If the patient consents for telephone contacts, schedule the next protocol-specified visit.

Patients will undergo the following assessments and procedures at Week 12 (Visit T4):

- Concomitant and prohibited medication review (ongoing)
- Assess AEs, including muscle-related AEs (ongoing)
- Weight
- Vital signs
- Clinical laboratory evaluations:
  - Hematology, blood chemistry, and urinalysis
  - Basic fasting lipids (TC, calculated LDL-C, HDL-C, non-HDL-C, and TG)
  - apoB
  - HbA1C
  - hs-CRP
  - PK sample (*patients randomized after Protocol Amendment 3 and subsequent amendments are excluded from PK sampling*)
  - Reserve sample
- Conduct diet and exercise counseling
- Return of IMP; assessment and recording of IMP compliance
- IWRS contact to obtain the MED ID number for IMP
- Dispense IMP
- Schedule next visit

Note: If this visit is being conducted at the site for patients who have consented to be followed for safety assessments, *including basic fasting lipids*, after withdrawing from IMP treatment, all assessments except for those procedures pertaining to apoB, hs-CRP, PK samples, reserve samples, and IMP management (IMP dispensing, IMP compliance, IMP accountability) should be completed.

Note: If this visit is being conducted by telephone contact for patients who have consented to be followed by phone for safety assessments after withdrawing from IMP treatment, collect information as reported by the patient regarding AEs, *concomitant medications*, and current health status.

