5.1 General Statistical Considerations

The ETC-1002 treatment group will be displayed in the tables, listings and figures (TLFs) as “bempedoic acid 180 mg.”

In general, all safety and PK data will be reported as observed. No imputation will be performed for missing data, except for the missing lipid efficacy data (Please refer to Section 5.3.2 for more details). Descriptive statistics (n, mean, standard deviation [SD], Q1, Q3, median, minimum, and maximum) will be calculated for continuous data. Minimum and maximum will be presented same number of decimal places as reported/collected, one additional decimal place for mean and median, and two additional decimal places for SD.

Categorical data will be summarized using n and percentage based on number of non-missing values. Percentage will be presented with one decimal place. The number of missing values will be presented as a separate category with no percentage, but only if 1 or more patients are missing data for the summary. Otherwise, all categories will be presented (even if no patients are counted in the category). Counts of zero in any category will be presented without percentage.

Data will be presented on listings in order of patient, assessment date and assessment (in order collected on CRF, unless specified otherwise). Dates will be presented in format DDMMYY YYYY.

Relative day calculations will be [date of interest – relative date + (date of interest >= relative date)]. This calculation will result in dates prior to the relative date being presented as negative days, and those occurring on or after the relative date as Day 1 or later, i.e., there will be no Day 0.

Baseline for fasting lipid parameters including LDL-C, TC, HDL-C, non-HDL-C, and Triglycerides are defined as the average of S1 and T1 values (last two non-missing values on or prior to Day 1). If only one value is available, the single value will be used as baseline. For other parameters including apoB and hsCRP, the baseline is defined as the last value/result where assessment date is less than or equal to the date of first study treatment, unless otherwise specified. If last dose of study treatment is missing, then the date of last visit at which study assessments were obtained on CRF will be used in its place.

The visit schedules and window are shown below.

Visit	S1	T1	T2	T3	T4	T5	T6	T7, EOS
Slotted Study Week	-2	0	4	8	12	24	36	52
Target Study Day	-16	1	29	57	85	169	253	365

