5.3 Primary Efficacy Endpoints and Analyses

For all efficacy analyses, the FAS will be used, with patients included in their randomized group, regardless of the treatment they actually received.

The primary and key secondary efficacy endpoints will be included in a step-down testing procedure to control overall type I error. Below endpoints will be tested sequentially at alpha level of 0.05. Each endpoint will be tested only if the previous endpoint achieved statistical significance.

1. percent change from baseline to Week 12 in LDL-C (primary efficacy)
2. percent change from baseline to Week 24 in LDL-C
3. percent change from baseline to Week 12 in non-HDL-C
4. percent change from baseline to Week 12 in TC
5. percent change from baseline to Week 12 in apoB
6. percent change from baseline to Week 12 in hsCRP

The clinical hypothesis being tested for each respective endpoint is that a treatment regimen with bempedoic acid 180mg daily in addition to other lipid modifying therapies (including statin) will result in higher reduction in respective lipid value than that from the lipid modifying therapy alone.

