5.3.1 Analysis for the Efficacy Parameters

Percent change in LDL-C, non-HDL-C, TC, and apoB at week 12 or week 24 will be analyzed using the analysis of covariance (ANCOVA) method. The ANCOVA model will include treatment, randomization stratum (from IWRs) as factors, and baseline value as covariate. In case of number of subjects within a stratum is too small for a meaningful analysis, the strata may be combined to obtain larger cell size. To account for the likelihood of unequal variances between the treatment groups, the ANCOVA model will be implemented within mixed model framework and the <repeated/group=> option will

be used to allow estimating the residual variances separately between the groups. The model assumptions for ANCOVA will be assessed and if these assumptions are severely violated, alternative non-parametric approach will be performed.

An example sas code for ANCOVA analysis is shown as below:

```
PROC MIXED DATA=adeff;
  class armcd stratum;
  model chg = blres armcd stratum/ solution ddfm=kenwardroger;
  repeated /group=armcd;
  lsmeans armcd / diff=control ('0') cl;
```

For hsCRP, a non-parametric (Wilcoxon rank-sum test) analysis with Hodges-Lehmann estimates and confidence interval will be performed because based on historical knowledge, publication precedence (Brendan et al., 2006) and recent data available, hsCRP is known to be skewed by extreme values and have non-normal distribution.

Efficacy data (actual value, change and percent change from baseline) from all visits will be presented using descriptive statistics using both conventional and standard units. A figure of mean (+/- SE) value or median (IQR) as appropriate, over time will be provided for these efficacy parameters.

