5.3.2 Missing Data Imputation

Missing data in efficacy endpoints included in the step-down procedure will be imputed using a pattern mixture model (PMM) to specify different imputation strategies depending on whether the patient is still on study treatment. Patients with missing lipid data at Week 12 who are no longer taking study treatment (date of last dose of IMP is < week 12 visit date -7) can be assumed to no longer be benefitting from study medication, and their missing value(s) can be assumed to be similar to those from the placebo patients who have data. To account for uncertainty, missing values will be imputed using multiple imputation via a regression based model including stratification factor, baseline value and week 12 value using data from placebo patients only. In this imputation model, treatment group will not be included as a factor.

Patients with missing lipid data at Week 12 who are still taking study treatment (date of last dose of study medication is \geq date of week 12 visit -7) can be assumed to continue to benefit from study medication, and their missing value(s) can be assumed to be similar to those who remain on study treatment and have data and as a result, missing lipid values will be imputed based on the observed values in their randomized treatment group. To account for uncertainty, missing values will be imputed using multiple imputation via a regression based model including data from both treatment groups. In this imputation model, treatment group will be included as a factor.

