5.3.3 Other Efficacy Endpoints

Percent change from baseline to week 52 in LDL-C will be analyzed using the ANCOVA method as described in section 5.3.1., using observed data (no imputation for missing data).

In addition, the same endpoint will be analyzed with patients in the FAS who did not receive additional lipid-lowering therapy by that time point (by week 24 and 52). Only observed case data will be used. Non-HDL-C, TC, ApoB and hsCRP at week 24 and 52 will be analyzed similarly using observed data.

The proportion of patients achieving LDL-C < 70 mg/dL at week 12, 24, and 52 will be summarized by treatment group and compared by Chi-sq test or fisher exact test. Only observed data will be used, i.e. the denominator will be number of patients who have LDL-C value at perspective time point.

TGs and HDL-C values at week 12, 24 and 52 will be summarized based on the FAS. For each parameter at each time point, the value of the parameter and the percent change from baseline in the parameter will be summarized by treatment group.

In cases where triglycerides (TGs) is >400 mg/dL or LDL-C is \leq 50 mg/dL, a measured LDL (LDL-M) will be used instead of LDL-C for the analysis of that time point. If both values are available, LDL-M will be used.

Baseline for each lipid is defined as the average of S1 (week -2) and predose Day 1/Week 0 values (the last two non-missing values on or prior to Day 1) with exception for apoB and hsCRP, for which predose Day 1 value will be used.

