5.3.4 Sensitivity Analysis for Efficacy Endpoints

- A sensitivity analysis for primary and key secondary endpoints included in the step-down procedure will be performed using the ANCOVA model with derived stratum instead of IWRS randomized stratum. For details of how the stratum are derived using concomitant medication and medical history, please see Appendix 3.
- The observed case data only (no imputations for missing data) analyses will also be used for sensitivity analyses for primary and key secondary endpoints. Observed data analysis will be conducted using FAS.
- On-treatment analysis will be using data collected during the treatment period only, i.e. up to the date of last dose of IMP +7 days (e.g. any efficacy data collected after 7 days post last dose of IMP will be excluded for efficacy analysis). On-treatment analysis will be conducted using SP for primary and key secondary endpoints
- By-visit summary for all efficacy endpoints (LDL-C, non-HDL-C, TC, ApoB, hsCRP, HDL-C and TGs) using on-treatment approach will be provided for both conventional and standard units.

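### Week-12 hsCRP, the last test in the alpha-controlled sequence, drops the baseline and stratum adjustment used for the other five; a rank-based adjusted test would be a cheap, optional gain in power.

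*SAP*

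**What the plan says.** SAP 5.3 lists six endpoints, each tested at 0.05 only if the one before it was significant. The sixth is "percent change from baseline to Week 12 in hsCRP".

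For LDL-C, non-HDL-C, TC and apoB, SAP 5.3.1 says: "The ANCOVA model will include treatment, randomization stratum (from IWRs) as factors, and baseline value as covariate". For the sixth it says: "For hsCRP, a non-parametric (Wilcoxon rank-sum test) analysis with Hodges-Lehmann estimates and confidence interval will be performed". The reason given is that hsCRP is skewed by extreme values. The SAP Summary of Changes, item 9, records the choice. The Protocol Synopsis (Key Efficacy Endpoints) had put hs-CRP in the adjusted ANCOVA, but SAP section 2 says the SAP prevails.

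A baseline hsCRP value is available. SAP 5.1: "For other parameters including apoB and hsCRP, the baseline is defined as the last value/result" on or before first treatment. SAP 5.3.3 gives the lipid baseline as an average, "with exception for apoB and hsCRP, for which predose Day 1 value will be used".

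Two further passages bear on hsCRP. SAP 5.3.4 opens with a sensitivity analysis of all step-down endpoints by ANCOVA with derived stratum. Its second bullet adds: "The observed case data only (no imputations for missing data) analyses will also be used for sensitivity analyses for primary and key secondary endpoints". SAP 5.3.2 prescribes imputation for every step-down endpoint. For patients off treatment this is "multiple imputation via a regression based model including stratification factor, baseline value and week 12 value using data from placebo patients only".

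**The concern.** Skewness is a reason to use ranks or logs. It is not a reason to leave out a covariate that is measured, prognostic and used for the other five endpoints. The cost would be power on the last confirmatory claim.

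Missing data are a linked gap that exists whichever test is used. At the Week-12 visit, patients already withdrawn from IMP complete "all assessments except for those procedures pertaining to apoB, hs-CRP, PK samples, reserve samples, and IMP management", so their hs-CRP is not drawn (nor is apoB). Imputation therefore matters here, yet SAP 5.3.2 states neither the scale nor how rank-test results are pooled. With log SD 1.1 assumed and correlations of 0.4 to 0.8, linear-regression imputation on the raw scale makes about 24 to 26% of imputed values negative.

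**Working it through.** **Inputs.** From the documents: 1300 and 650 patients (SAP 4.4) and alpha 0.05 (SAP 5.3). Two-sided testing is assumed, because the SAP states it only for the adverse-event calculation. The documents contain no hsCRP power figure to reproduce. Also assumed: log SD at Day 1 of 1.1; correlation r of 0.4, 0.6 or 0.8 between log Day 1 and log Week 12; ratio k of the Week-12 to the Day-1 log SD of 1 or 1.25; and a log effect of -0.12, which is a reduction of 1 - exp(-0.12) = 11.3%.

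**Step 1. What the planned test does with baseline.** Percent change is an increasing function of log(Week 12) - log(Day 1), so the two have the same ranks. The planned test therefore uses baseline with its log-log slope fixed at 1. Power is lost only to the extent that the true slope, rk, differs from 1.

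**Step 2. Relative efficiency.** With log SD s at Day 1, the variance is s²(k² + 1 - 2rk) for the planned comparison and s²k²(1 - r²) after baseline adjustment. The ratio of adjusted to planned variance is k²(1 - r²)/(k² + 1 - 2rk).

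| r | k = 1 | k = 1.25 |
|---|---|---|
| 0.4 | 0.70 | 0.84 |
| 0.6 | 0.80 | 0.94 |
| 0.8 | 0.90 | 1.00 |

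At k = 1 this reduces to (1 + r)/2.

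**Step 3. Power.** Under normal log errors, power is about Φ(0.12 × √(3/π)/(SD × √(1/1300 + 1/650)) - 1.96), with √(3/π) = 0.977 and the second root equal to 0.0480. For r = 0.6 and k = 1:
- Planned: SD = 1.1 × √0.8 = 0.984; 0.12 × 0.977/(0.984 × 0.0480) = 2.48; power Φ(0.52) = 70%.
- Adjusted: SD = 1.1 × √0.64 = 0.88; the same expression gives 2.77; power Φ(0.81) = 79%.

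Simulation of the Wilcoxon test against the same test on log-baseline-and-stratum residuals (4,000 runs per setting, Monte Carlo error at most 0.8 point) agrees:

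| r | k = 1, planned to adjusted | k = 1.25, planned to adjusted |
|---|---|---|
| 0.4 | 53.6 to 68.4% | 42.8 to 49.2% |
| 0.6 | 70.6 to 78.6% | 56.6 to 59.4% |
| 0.8 | 93.4 to 95.3% | 84.8 to 84.4% |

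At a 20% reduction (log effect -0.223, k = 1), power goes from 96.4 to 99.6%, 99.8 to 100% and 100 to 100%.

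**Step 4. The method to recommend.** ANCOVA on ranks (rank of baseline plus stratum) at a 10% reduction, with 5% missing assumed and 1,500 runs, gave 40 to 53%, 59 to 67% and 85 to 88% at r = 0.4, 0.6 and 0.8. It matched the log-residual test under normal log errors. With 5% of values inflated fifty-fold at r = 0.8 and an 11% reduction, the planned test had 82.6% power, the log-residual version 77.9% and the rank ANCOVA 87.8%. Stratification alone (van Elteren test) moved power by less than 1 point, so the gain comes from baseline.

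**Step 5. Validity.** Null rejection over 8,000 runs was 4.7 to 5.4% for the Wilcoxon and 4.6 to 4.8% for the rank ANCOVA.

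**The case against.** The strongest case for leaving the plan alone is that a simple rank test is legitimate, stated in advance and explained. Percent change already brings baseline in. Every input to the power comparison is assumed, and the gain disappears in some plausible settings: recent events and surgery are excluded only at entry, so more spread at Week 12 (k above 1) is credible. A log-baseline adjustment would also do worst under the extreme values that worry SAP 5.3.1, as the fall to 77.9% shows, and would replace percent change with a ratio.

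Most of this stands. It limits the point to an option and rules out the log-residual method. It does not rescue the link from skewness to dropping the covariate, because a rank-based adjustment handles extreme values and keeps the percent-change endpoint.

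A reader might also infer that hsCRP has no adjusted analysis anywhere. The documents do not support that: the first bullet of SAP 5.3.4, read literally, applies ANCOVA with derived stratum to it, though only as a sensitivity analysis and in tension with 5.3.1. Nor was the choice hidden. SAP 4.6 does not list it among changes from the protocol, but the Summary of Changes does.

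**Conclusion.** The point holds as an optional efficiency improvement. Under the stated assumptions, baseline adjustment is worth about 14, 8 and 2 points of power at r = 0.4, 0.6 and 0.8 for an 11% reduction with equal log SDs. It is worth about 3 and 0 points at r = 0.6 and 0.8 when the Week-12 log SD is 25% larger, and little at a 20% reduction.

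It would be wrong to infer that the planned test is invalid, that type I error is inflated or that other claims are at risk. Rejection under the null is close to 5%, and hsCRP is last in the sequence, so a miss there blocks nothing. The missing imputation scale and pooling rule are a real gap, but they are not evidence for the adjustment.

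**What to change.** - **SAP 5.3.1:** test Week-12 hsCRP by ANCOVA on the ranks of percent change, with treatment, IWRS stratum and the rank of Day 1 hsCRP. Keep the Hodges-Lehmann estimate and confidence interval on percent change as the reported effect. The endpoint wording in SAP 3.3.2 and 5.3 and in Protocol 12.6.1 then needs no change.
- **SAP 5.3.4:** name the unadjusted Wilcoxon test as an hsCRP sensitivity analysis, which preserves integration with the other phase 3 studies. Reconcile the first bullet with 5.3.1 by saying whether ANCOVA with derived stratum applies to hsCRP, and on what scale.
- **SAP 5.3.3:** state whether hsCRP at Weeks 24 and 52 follows the same method.
- **SAP 5.3.2:** impute hsCRP on the log scale, pool the rank-ANCOVA treatment coefficient by Rubin's rules, and say how the Hodges-Lehmann estimate is combined across imputations.

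The cost is a few sentences and a few lines of code, settled before database lock and unblinding, with no new data. The downside is that the p-value comes from an adjusted rank model while the reported estimate is unadjusted, so the two can occasionally disagree near 0.05. The SAP should say that the p-value governs the step-down decision.

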5.3.2 Missing Data Imputation

Missing data in efficacy endpoints included in the step-down procedure will be imputed using a pattern mixture model (PMM) to specify different imputation strategies depending on whether the patient is still on study treatment. Patients with missing lipid data at Week 12 who are no longer taking study treatment (date of last dose of IMP is < week 12 visit date -7) can be assumed to no longer be benefitting from study medication, and their missing value(s) can be assumed to be similar to those from the placebo patients who have data. To account for uncertainty, missing values will be imputed using multiple imputation via a regression based model including stratification factor, baseline value and week 12 value using data from placebo patients only. In this imputation model, treatment group will not be included as a factor.

Patients with missing lipid data at Week 12 who are still taking study treatment (date of last dose of study medication is \geq date of week 12 visit -7) can be assumed to continue to benefit from study medication, and their missing value(s) can be assumed to be similar to those who remain on study treatment and have data and as a result, missing lipid values will be imputed based on the observed values in their randomized treatment group. To account for uncertainty, missing values will be imputed using multiple imputation via a regression based model including data from both treatment groups. In this imputation model, treatment group will be included as a factor.

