#### Renal Safety

Baseline estimated glomerular filtration rate (eGFR) will be summarized by treatment group for actual value and for baseline eGFR categories. Shift tables of eGFR category from baseline over the study, will be provided by treatment group. Shift tables of urine protein (negative/positive) from baseline over the study, will be provided by treatment group. Values of CK over the study will be summarized by treatment group and by baseline eGFR category. Finally, muscle-related AEs will be summarized by treatment group and by baseline eGFR category.

Clinical Endpoints

*Clinical endpoints* will be monitored and adjudicated by an independent blinded expert CEC for ongoing studies the ETC-1002 program. Adjudicated *clinical endpoints* will be summarized by event type and treatment group. Additional details regarding *clinical endpoints* and *clinical endpoint* definitions will be included in CEC charter.

Neurocognitive Events

Neurocognitive events will be identified and evaluated by routine safety monitoring of PE findings and AEs. Summarization of neurocognitive events will occur using prespecified Medical Dictionary for Regulatory Activities (MedDRA) terms and will be performed by SOC, severity, and relationship to study drug for each treatment group

Key Efficacy Endpoints

*Percent change from baseline to Week 12 or Week 24 in LDL-C, non-HDL-C, TC, apoB, and hs-CRP will be analyzed using analysis of covariance (ANCOVA), with treatment and randomization strata (patient's CV risk and baseline statin dose) as factors and respective baseline value as a covariate. The FAS will be used. Missing data for these endpoints will be imputed using multiple imputation taking account for treatment adherence.*

Other Efficacy Endpoints

*LDL-C, HDL-C, TG, TC, non-HDL-C, hs-CRP, and apoB values at other time points will be summarized and analyzed similarly to the key lipid endpoints. In addition, a summary using the FAS, excluding patients who received additional lipid-lowering therapy by that time point (by Week 24 for the Week 24 time point; by Week 52 for the Week 52 time point), will be provided. For both summaries, only observed case data will be used (no imputation for missing data).*

Additional post-randomization adjunctive lipid-modifying therapy

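### Does the imputation rule in SAP 5.3.2 need rewriting because its on/off-treatment cutoff and placebo-based model are spelled out for Week 12 only?

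*SAP*

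**What the plan says.** SAP 5.3.2 opens with its scope: "Missing data in efficacy endpoints included in the step-down procedure will be imputed using a pattern mixture model (PMM"; the strategy is chosen "depending on whether the patient is still on study treatment". The step-down list in SAP 5.3 has six endpoints. Five are at Week 12 and one is not: "2. percent change from baseline to Week 24 in LDL-C".

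The operating detail in 5.3.2 is then written for Week 12. A patient is off treatment if the "date of last dose of IMP is < week 12 visit date -7", and on treatment otherwise. Off-treatment patients are imputed "via a regression based model including stratification factor, baseline value and week 12 value using data from placebo patients only". On-treatment patients are imputed from a model that uses both arms, with treatment as a factor.

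The protocol synopsis (Key Efficacy Endpoints), which names both Week 12 and Week 24, gives the same principle: "Missing data for these endpoints will be imputed using multiple imputation taking account for treatment adherence". Protocol 12.6.1 leaves the details to the SAP.

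SAP 5.1 lists target Days 85 and 169. Its only date fallback is for a missing last dose: "then the date of last visit at which study assessments were obtained on CRF will be used in its place". It has no counterpart for a missed visit. The on-treatment sensitivity analysis in SAP 5.3.4 uses data "up to the date of last dose of IMP +7 days".

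**The concern.** Three details seem to be missing from a confirmatory analysis.

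- **Missed visit.** The cutoff needs a Week 12 visit date, yet a missed visit is a main reason for missing data. This touches all six endpoints.
- **Week 24 cutoff.** None is written, although Week 24 LDL-C gates the four endpoints below it.
- **Week 24 model.** The placebo-based model names the Week 12 value. An analyst could replace it with the Week 24 value, or keep it as a predictor. Keeping it would carry an on-drug Week 12 result into the imputation for someone who stopped after Week 12, whom 5.3.2 assumes no longer benefits. That would favour ETC-1002.

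If these choices moved the estimate materially, the result would depend on decisions that the SAP leaves open.

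**Working it through.** **Reading the text.** In the Week 12 model the Week 12 value is the quantity being imputed; the predictors are stratum and baseline. The Week 24 counterpart is therefore stratum, baseline and Week 24 value. Keeping the Week 12 value as a predictor would change its role and would contradict the premise that off-treatment patients resemble placebo patients. The Week 24 cutoff follows in the same way, and its 7 days match the rule in 5.3.4.

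**Dropout (SAP 4.4).** The plan's exposure table reproduces: 1300 × 0.925 = 1202.5 (stated 1,202), 650 × 0.925 = 601.25 (601), 1300 × 0.90 = 1170, 650 × 0.90 = 585. Assuming linear accrual over the first 182 days, the daily rate is 0.075/182 = 0.0412%.

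**Who cannot be classed after a missed visit.** The cutoff is the visit date minus 7. The scheduled ranges are Day 85 ± 3 and Day 169 ± 7 (Protocol Appendix 1, SAP 5.1).

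| | Week 12 | Week 24 |
|---|---|---|
| Visit date | Day 82 to 88 | Day 162 to 176 |
| Cutoff | Day 75 to 81 | Day 155 to 169 |
| Last dose with class open | Days 75 to 80 (6 days) | Days 155 to 168 (14 days) |
| Share of an arm | 6 × 0.075/182 = 0.25% | 14 × 0.075/182 = 0.58% |
| ETC-1002 patients (of 1300) | 3.2 | 7.5 |
| Largest shift, effect 10 to 20 points | 0.02 to 0.05 | 0.06 to 0.12 |

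The shift is share × effect: it moves every such patient from treatment-based to placebo-based imputation. The documents give no LDL-C effect or SD, so both are assumed here.

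**These are upper figures.** They suppose that nobody in the band is measured and nobody has a usable date. In fact, stopping study drug triggers the Protocol 10.2.8 assessments, including fasting lipids, and patients are asked to continue lipid visits (Protocol 10.3.1). Samples are not drawn from unfasted patients (Protocol 11.1.6.2 and 11.7.2), so some missing values come with a dated visit. Telephone follow-up also has a date.

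**The disfavoured Week 24 model.** It matters for patients who count as on treatment at Week 12 and off treatment at Week 24. At the target days that means last doses from Day 78 to Day 161, or 84 days: 84 × 0.075/182 = 3.46%, 45 ETC-1002 patients. With an assumed slope of Week 24 on Week 12 of 0.5 to 0.8, the two readings differ by 0.0346 × 0.5 × 10 = 0.17 to 0.0346 × 0.8 × 20 = 0.55 points if none is measured at Week 24. If a quarter are unmeasured, the difference is 0.04 to 0.14.

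**Scale.** The standard error is SD × √(1/1300 + 1/650) = SD × 0.0480. The 95% half-width is 1.96 × 0.0480 × SD = 1.88 (SD 20) to 2.82 (SD 30). On the least favourable inputs (effect 10, SD 30), z = 10/1.441 = 6.9. Taking off 0.0346 × 0.8 × 10 = 0.28 points leaves z = 9.72/1.441 = 6.7.

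**The case for a change.** The strongest case is one of principle. These are alpha-controlled tests, Protocol 12.6.1 defers the model to the SAP, and an imputation should be reproducible from the SAP without analyst choice. That stands as a remark on drafting.

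The size can also be made to look larger. If a missed visit could be dated anywhere in the SAP 5.1 analysis windows (Days 72 to 127 and 128 to 211), the open bands become Days 65 to 119 and 121 to 203. They then hold 55 × 0.075/182 = 2.27% (about 29 ETC-1002 patients) and 62 × 0.075/182 + 21 × 0.025/183 = 2.84% (about 37). The shifts are 0.23 to 0.45 and 0.28 to 0.57 points. But those windows slot visits that took place; an analyst dating a missed visit would turn to the schedule. Even these figures are well inside the confidence half-width.

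For apoB and hs-CRP, samples are not taken after study drug is stopped (Protocol 10.2.5), so assuming no measured values is closer to the truth there. A patient who attends still supplies a visit date, however, so the cutoff can be applied.

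The point about an on-drug Week 12 value is correct in direction. The section's own premise excludes that reading.

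**Conclusion.** The wording is incomplete, but the method is not in doubt. SAP 5.3.2 states the principle for every step-down endpoint, and an analyst can fill in Week 24 and the missed-visit date from the section itself and the target days in SAP 5.1. On the scheduled visit ranges the open choice concerns about 3 ETC-1002 patients at Week 12 and 7 to 8 at Week 24, worth at most 0.05 and 0.12 points of LDL-C change. Even the reading that contradicts the section's premise moves Week 24 by at most about 0.55 points. No result in the hierarchy is expected to change.

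This rests on the planned dropout accruing linearly, an effect of 10 to 20 points, an SD of 20 to 30, a slope of 0.5 to 0.8 and placebo-like values off drug. The observed-case and on-treatment analyses in SAP 5.3.4 do not use the imputation rule, so they would show part of any dependence on it. No change to the plan follows.
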